1 BACKGROUND

Intracranial aneurysms (IA) are common. Their prevalence is 3.2% in healthy people aged 50 (Vlak 2011). They occur with increasing frequency from the third decade onwards. They are usually asymptomatic and are detected incidentally on scans (usually MRI or CT) done for other reasons. Some can rupture and cause subarachnoid haemorrhage (SAH). The incidence of SAH is much lower at 9.1 per 100,000 person years (de Rooij 2007), reflecting a relatively low rate of IA rupture estimated at 1.4% per annum (Greving 2014).

Unruptured IAs (UIAs) can be treated prophylactically to prevent rupture with open microsurgery to apply a clip to occlude the aneurysm neck, or endovascularly to insert coils to fill the aneurysm sac. However, it is hard to justify treating all UIAs given these procedures carry a 5% or more risk of permanent morbidity or mortality, and very few rupture. It is therefore necessary to identify UIAs at high risk of future rupture for treatment.

An international attempt at a randomized controlled trial to address which patients benefit from treatment was stopped due to poor recruitment (just 80 patients consented to the study over 3 years out of a planned study size of 2000 (Raymond 2011)) and is unlikely to repeated. Therefore, treatment decisions are made based on what is known about the natural history of UIAs. The problem is that data on the natural history of UIAs is inadequate to inform major treatment decisions such as this.

Only one large multicentre prospective cohort has studied a population of UIAs applicable to the UK. The International Study of Unruptured Intracranial Aneurysms (ISUIA) was an international multicentre prospective cohort study which documented a strong relationship between aneurysm size (maximum diameter in any dimension at baseline) and SAH (Wiebers 2003). Five year SAH rates were 0% and 2.6% for IAs <7mm and 7-12mm respectively. ISUIA received extensive criticism both before (Ausman 2002), and after publication of results (Raymond 2008). A large number of patients were selected for treatment (58%), and of those selected for conservative management, many went on to have their UIA treated (32%) so that overall 72% were treated. This selection was not random, and the study population was not representative of all UIAs.

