4 RESEARCH QUESTION/AIM(S)

Primary Aims:

Aim 1 - To validate the PHASES score in a UK population.

- Aim 2 To develop a new prediction model including all described predictors of risk.
- Aim 3 To report long-term risk of aneurysm rupture.

Secondary Aims:

Aim 4 – To develop risk models of aneurysm growth.

Aim 5 – To evaluate the efficacy of aneurysm screening regimens.

Aim 6 – To develop and evaluate new radiological predictors of aneurysm growth and rupture.

5 STUDY DESIGN and METHODS of DATA COLLECTION AND DATA ANALYIS

Data Collection – Baseline data – local neurosciences units Patients will be identified by members of the clinical care team and record:

- NHS number
- Name
- Date of birth
- Post code

These patients will be allocated a study number for pseudonymisation. This data will not be otherwise kept or used for other research purposes.

Further data will be collected from patient's case notes (either electronic or paper based as appropriate). A separate data definitions manual will be produced. All data collectors will be provided with a mandatory education module and correctly collect data from test cases before data collection.

The core covariates for each patient at time of diagnosis will be:

- Date of first diagnosis of aneurysm (date of first CTA/MRA/DSA or where not available date of first MDT or clinic appointment whichever is earlier)
- Date of inclusion in the study (date of first CTA/MRA/DSA or where not available date of first MDT or clinic appointment that lies within the unit's search period)
- Hypertension: a co-morbidity of hypertension or regular use of anti-hypertensive medication at time of diagnosis.
- Age: in years at time of diagnosis of aneurysm on angiographic imaging
- Gender:
- Site: anterior cerebral artery (including anterior communicating and pericallosal arteries), internal carotid (including bifurcation, ophthalmic, superior hypophyseal), MCA (including M1 segment and bifurcation), posterior communicating and posterior circulation (including vertebral, basilar, cerebellar and posterior cerebral arteries).
- Aneurysm size: the longest aneurysm dimension recorded to the nearest millimetre as described by the MDT discussion or where not available from the reporting radiologist at time of diagnosis or where not available from the clinic letter.
- Previous aneurysmal subarachnoid haemorrhage: confirmed diagnosis of aneurysmal SAH in the patient's medical history.

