subarachnoid haemorrhage other or unspecified and they subsequently died within 30 days (based on the very low rate of mortality from non-aneurysmal SAH) and did not have any additional codes for trauma indicating a non-aneurysmal event.

Data collection - other considerations - central HES ONS data

Last follow-up for each patient will be set as the time at which the HES search was performed, or the patient was unregistered with a GP in the UK or date of death, or the aneurysm was treated, whichever is earliest.

Additionally, we will record

- 1. race
- 2. I10 essential (primary) hypertension
- 3. Z72.0 tobacco use
- 4. F17.2 tobacco dependence

And use these to complete any missing baseline data. Where baseline data and HES conflict, the baseline data will be used. Where neither is available, after assessment for any bias (missing completely at random MCAR, missing at random MAR, missing not at random MNAR) multiple imputation will be used.

Statistical analysis - Aim 1 - PHASES validation

The PHASES study provides the coefficients from their Cox regression model and baseline survival at 5 years that allows the absolute 5-year risk of rupture, to be calculated for all patients who are not censored before 5 years, using age, whether the patients has hypertension, history of SAH, size of aneurysm (3 categories) and location of aneurysm. The time to censoring will be calculated (death or date of HES search or date unregistered from GP practice whichever is first) to ensure 5 years of follow up if rupture has not occurred. Discrimination will be assessed using Harrell's C-index of concordance and Royston and Sauerbrei's D statistic. Calibration will be assessed at the 5 year time point using the method in Royston (2014). These will be used to calculate the number of SAH events per 5 years for each PHASES score (0 to 12+) and expressed as a percentage with 95% confidence interval to compare to the PHASES estimates.

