7.2 Sampling

7.2.1 Size of sample

Sample Size

There are no accepted methods for power calculation for validation studies of prognostic models. Therefore, usually the rule of thumb to have ten events for every covariate tested is applied.

For Aim 1, 6 covariates will be tested suggesting at least 60 SAHs will need to be captured. ISUIA recorded 51 ruptures in 1692 patients over 4.1 years. Sixty events may therefore be expected in 1,990 patients with 8,161 years of follow up.

For Aim 2, 120 events will need to be observed to account for the 6 additional commonly occurring covariates which would be expected in 3,981 patients with 16,332 years of follow up.

For autosomal dominant polycystic kidney disease (ADPKD) which has a low incidence, larger numbers of patients will be needed. Ten events in ADPKD are expected in 1360 patient years of follow up assuming the risk of SAH is not elevated and similar to the general population. However, 16,332 years follow up would only yield 195 years in patients with ADPKD (based on a population study which found 53/4436 IAs had ADPKD (Nurmonen 2017) and consistent with pilot data where 11/1025 cases examined to date had ADPKD). Therefore 113,905 years of follow up would be required to capture 10 ruptures amongst 1,340 years follow up in ADPKD patients. This would equate to 22,781 patients with 5 years of follow up (or applying the slightly looser rule of 5 events per prognostic factor this would require 56,952 years of follow up with 11,391 patients).

In a local pilot 1,415 cases were identified over 14 years in a population of 3 million with an anticipated 6,000 years of follow up. Extrapolating to England, Wales and Scotland 31,130 patients with 132,200 years follow up are available - well in excess of the target of 8,161 to validate PHASES in the general population, as well as the 16,332 to test the additional variables, but only just sufficient to answer the role of rarer predictors such as ADPKD. For reference PHASES was based on 29,166 years of patient follow up. Therefore, all cases that can be identified in England and Wales will be sought up to a maximum of 22,781.

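### Rounding aneurysm size to the nearest millimetre before assigning PHASES size categories can misclassify sizes near a whole-millimetre limit in one direction, and the lost decimal cannot be recovered at analysis

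*Protocol*

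**What the plan says.** In Protocol section 5, under the core covariates, aneurysm size is "the longest aneurysm dimension recorded to the nearest millimetre as described by the MDT discussion". The fallback sources are given as "where not available from the reporting radiologist at time of diagnosis or where not available from the clinic letter". The precision of these sources is not stated.

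Under Statistical analysis, Aim 1, the PHASES coefficients are applied using, among other items, "size of aneurysm (3 categories) and location of aneurysm". Observed 5-year SAH percentages are then tabulated for each PHASES score and compared with the PHASES estimates. The protocol does not print the limits of the three size categories or say to which side a boundary value belongs.

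The only size limits in the document come from the background account of ISUIA, not from PHASES: "Five year SAH rates were 0% and 2.6% for IAs <7mm and 7-12mm respectively".

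**The concern.** Size is one of the six PHASES items, and validating PHASES is the first primary aim. The protocol coarsens the measurement at data entry and then cuts it. If the cut falls on a whole millimetre, all the rounding error at that limit goes one way and does not cancel. Patients then receive a size category, and so a predicted risk, that their reported measurement does not support. An artefact of this kind in the calibration results could be mistaken for a real difference in rupture risk between the UK and the PHASES cohorts.

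This is not a matter that an analysis plan can settle later. The rounding rule is a data-collection rule, and a decimal that was never entered is not available to the analyst.

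**Working it through.** **The plan's own figure.** Section 7.2.1 says that "ISUIA recorded 51 ruptures in 1692 patients over 4.1 years". For 60 events this gives 60 / (51/1692) = 1,990.6 patients and 1,990.6 × 4.1 = 8,161 years, matching the stated 1,990 and 8,161. The point below neither disputes nor depends on this figure.

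**Direction of the rounding error.** Every size from 1.0 to 29.9 mm in steps of 0.1 mm was rounded to the nearest millimetre (half up) and cut at a whole-millimetre limit c.

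| Form of the limit | Moves up at c = 7 | Moves down at c = 7 |
|---|---|---|
| below c / c or more | 6.5 to 6.9 mm | none |
| c or less / above c | none | 7.1 to 7.4 mm |

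The pattern is the same at 10, 12, 13 and 20 mm. The error is one-sided under both forms, but the form decides the sign.

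**Size of the effect.** Inputs from the protocol are the ISUIA 5-year rates, 0% below 7 mm and 2.6% for 7-12 mm (read here as 7 to under 13 mm). Everything else is assumed, because the protocol gives no size distribution: log-normal size with median m from 3.5 to 6 mm and log-SD s from 0.4 to 0.6, the form below 7 / 7 or more, and a decimal in every source.

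- Share of the cohort that crosses: M = Φ(ln(7/m)/s) − Φ(ln(6.5/m)/s)
- Share recorded as 7-12 mm: R = Φ(ln(12.5/m)/s) − Φ(ln(6.5/m)/s)
- Part of the recorded band that is truly below 7 mm: f = M/R
- Observed risk if risk is a step at 7 mm: 2.6% × (1 − f)

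For m = 4.5 and s = 0.5: M = 0.8116 − 0.7690 = 0.0426; R = 0.9795 − 0.7690 = 0.2105; f = 0.0426/0.2105 = 0.202; risk = 2.6% × 0.798 = 2.07%.

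| m (mm), s | M | f | Step risk | Smooth risk |
|---|---|---|---|---|
| 3.5, 0.4 | 1.9% | 32% | 1.77% | 2.17% to 2.44% |
| 4.5, 0.5 | 4.3% | 20% | 2.07% | 2.21% to 2.45% |
| 6, 0.4 | 7.1% | 18% | 2.13% | 2.24% to 2.47% |
| 6, 0.6 | 4.8% | 14% | 2.23% | 2.23% to 2.46% |

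Smooth risk means risk proportional to size to the power 1, 2 or 3, scaled to 2.6% in the true 7-12 mm band. In that case the group below 7 mm also loses its highest-risk members, and its observed risk falls by about 2% to 15% in relative terms.

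**Share of sources with decimals.** M scales with that share. If half the sources carry a decimal, the crossing share is about 1% to 3.5% of the cohort. If none do, the rule changes nothing.

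**The case against.** A reader might infer more than the protocol supports: that misclassification is only upward, that it dilutes only the higher PHASES categories, and that the validation will therefore show PHASES overpredicting. The case against that reading is strong.

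- **Limits.** The protocol gives no PHASES limits and no boundary side. Whole-millimetre limits are an assumption, and the opposite boundary convention reverses the direction.
- **Other error.** One-sidedness applies to rounding alone. Reading error, and differences between the MDT, radiologist and letter, can go either way.
- **Source precision.** Nothing shows that the sources carry decimals, so no effect at all is possible.
- **PHASES cohorts.** Bias against PHASES requires its cohorts to have been recorded more finely or rounded differently. If they were rounded alike, the bias shrinks. The protocol is silent on this.
- **Step risk.** The lowest figures give a 6.9 mm aneurysm a risk of 0% and a 7.0 mm aneurysm the full 2.6%. The background section itself questions the ISUIA rates. Smooth risk gives a smaller fall, and it affects the category below the limit too.
- **Aim 2.** Loss of precision there is trivial. Rounding variance is 1/12 mm², against a size variance of about 4.4 to 17 mm² for medians of 4 to 6 mm and log-SD of 0.45 to 0.55. That is roughly 0.5% to 2%.

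All of this stands, and it limits the claim. It can also be said that finer rules may sit elsewhere, since "A separate data definitions manual will be produced". That manual is not shown, and it cannot be assumed to override an explicit rule in the protocol. None of these objections gives a reason to discard a decimal that the data collector has in front of them.

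**Conclusion.** The point holds in a limited form. The protocol rounds size at entry and categorises it afterwards. Where a source gives a decimal and a limit is a whole millimetre, this produces avoidable one-sided misclassification that feeds the Aim 1 calibration.

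The effect cannot be sized from the protocol. The range of 1.8% to 2.5% against 2.6% rests on the assumed size distribution, a lower-closed 7 mm limit borrowed from ISUIA, and decimals in all sources, so it is an upper-end illustration. Neither the sign of the error nor a bias against PHASES is established. Severity is minor to moderate: the size is uncertain, but the information is lost for good and keeping it is nearly free.

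**What to change.** In section 5, replace recording to the nearest millimetre with recording as reported, to 0.1 mm where given, and add a flag for sources that give whole millimetres only. State the PHASES size limits and the side on which a boundary value falls, and assign the category from the unrounded value. Use the unrounded value in the Aim 2 model as well; the gain there is small.

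For data already entered as rounded values, add a sensitivity analysis that reassigns sizes recorded exactly at a limit to the neighbouring category, and report calibration both ways. Moving all of them overcorrects, because some were classified correctly, so the two results bracket the effect of rounding at that limit.

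For new data the cost is one field format in the protocol and the data definitions manual, with no extra reading of notes. Decimals already discarded can be recovered only by returning to the notes, and the sensitivity analysis avoids that. The downside is that precision will differ between sources; the flag makes this visible.

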- A) The only study with a genetically similar population accepting the likelihood that in a predominantly Northern American cohort with high treatment rates a disproportionate number of high risk aneurysms (for example with dome irregularity and blebs) were treated before entry to the study.
- B) The only study with no selection or follow up bias accepting that this study found a markedly higher rate of rupture (26% vs 0% in ISUIA over 30 years) for the most common types of aneurysm (Juvela 2013), but that this difference may also be due to genetic or environmental differences in the Finnish population.
- C) The largest available study accepting the inherent biases introduced by combining studies of different and non-overlapping populations all with markedly different risk profiles.

There is therefore a pressing need for more research into the natural history of unruptured aneurysms. Specifically, the PHASES score, whilst used by 24 out of 30 neurosurgery units in the UK (unpublished data), has never been validated for use in a UK population. **Aim 1 - To validate the PHASES score in a UK population.**

The PHASES model only used 6 available patient and aneurysm characteristics for prediction. There are many more that are believed to have a large influence on risk but have not been considered. Examples include aspirin use, statin use, smoking, aneurysm irregularity, multiple aneurysms, family history of aneurysms/SAH and polycystic kidney disease. Therefore:

Aim 2 - To develop a new prediction model including all described predictors of risk.

Most clinicians believe that rupture risk is higher early after aneurysm formation and reduces with time. However, practically all clinical decisions are made by projecting estimates of short-term risk over a patient's lifetime (assuming a constant risk). For example, 68% of patients in PHASES came from a study with just 1.0 year of follow up which is reported as a 5 year risk in PHASES which is then extrapolated by clinicians to 30 year/lifetime risks. Therefore, very small errors in 1 year rates can lead to very large errors in lifetime risks. Moreover, none of the studies accounted for whether the aneurysm was a new diagnosis at time of recruitment or not. Data is therefore needed to determine the long-term risks of UIAs and assess if the early and late risks are the same. Therefore: **Aim 3 - To report long-term risk of aneurysm rupture.**

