- Population: European/North American, Finnish, Japanese (where race cannot be confirmed it will be assumed to be non-Finnish and non-Japanese on the basis that there is a low incidence of these populations in the UK and their presence would usually be considered noteworthy in a clinical note.

The additional desirable covariates at time of diagnosis will include:

- aspirin use any dose used >3* per week
- statin use any statin use >3* per week
- smoking history non-smoker, ex-smoker, current smoker
- Aneurysm multiplicity record number of intra-dural aneurysms the patient has (treated or untreated)
- Family history number of 1 first degree and second degree relatives with UIA/SAH
- History of Autosomal Dominant Polycystic Kidney Disease yes, no
- Aneurysm location subclassification ICA paraclinoid (ophthalmic and superior hypophyseal) ICA (PCom), ICA other (anterior choroidal and bifurcation), ACA ACOM, ACA pericallosal, MCA, Posterior (basilar termination), Posterior (SCA), Posterior (AICA) Posterior (PICA)
- Bleb or irregularity of aneurysm recorded as present or absent from radiology report only. If not mentioned in report assumed to be absent. If no radiology report available, then recorded as NA.
- New/known diagnosis: patients in whom the aneurysm was known prior to the search period will be recorded as known diagnosis and otherwise as new diagnosis.

Data collection – aneurysm rupture/censoring events – local neurosciences units

At the time of baseline data collection locally available follow up will be recorded which will include:

• Date of last follow-up

- Date of death (if applicable)
- Cause of death (if applicable)
- Date of SAH (if applicable)
- Location of aneurysm causing SAH (if applicable)
- Date of aneurysm treatment (if applicable)
- Reason for aneurysm treatment (if applicable)

This data will be used for quality control of subsequent HES searches.

Data collection - aneurysm rupture/censoring events - central HES ONS data

Upon collection of all baseline data, a search of the Hospital Episode Statistics (HES) and Office for National Statistics (ONS) databases using the patient's NHS numbers be conducted. The use of a HES and ONS search is designed to maximise the identification of rupture events which are not treated in neurosurgical unit as subarachnoid haemorrhage. It will thus identify events managed in a district general hospital or those who die pre-hospital.

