A new risk prediction model for rupture will be developed using the total data set, including the additional possible risk factors. The Cox regression model will be used for risk of rupture. The absolute risks can be estimated at relevant time intervals, 2, 5 and 10 years. Numbers of missing values will be summarised for each factor. Multiple imputation will be used to replace missing values. Discrimination of the final model will be assessed with the Harrell's c-statistic. Internal validity will be assessed by bootstrap resampling.

Additionally, the following sensitivity analyses will be performed:

In view that a significant number of aneurysms are anticipated to have grown and subsequently treated on follow up, any cases noted to have undergone treatment for aneurysm growth will be included in a model predicting the risk of rupture or treatment for aneurysm growth. In view that it is anticipated that a number of unexplained deaths will be captured where it will not be possible to resolve if the cause was SAH or not, a model predicting aneurysm rupture or unexplained or unattended death (R 96 and 98) will be built.

Statistical analysis - Aim 3 - Long term rupture rates

It is anticipated that initially follow up times will range from months to 15 years. This will be insufficient to definitively answer what the long term risks posed by aneurysms are. However, a model will be built including a term for new diagnosis vs known diagnosis. This will establish if rupture rates are similar between patients with new and prior diagnoses.

All patients, including those who underwent aneurysm occlusion, will be included in time-to-event analysis which will cover the whole duration of available follow-up. This will include Kaplan-Meier and proportional hazards models for univariate and multivariate survival curve fitting. A cumulative Hazard plot will be used to assess if rupture risk is constant or varies with time from diagnosis.

Longer term, HES searches will be repeated periodically using unique HES identifiers generated by DARS at the first HES search. These searches will identify any late events of SAH due to aneurysm rupture and models will be built to predict true long-term risk.

Data management

Patient confidentiality

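### Coding a silent radiology report as 'irregularity absent' merges stated-smooth with not-commented-on aneurysms, and may bias the irregularity effect in the Aim 2 model

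*Protocol*

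**What the plan says.** Section 5 (Data Collection – Baseline data, additional desirable covariates) gives the source and the levels: "Bleb or irregularity of aneurysm recorded as present or absent from radiology report only". It then gives the rule for silence: "If not mentioned in report assumed to be absent. If no radiology report available, then recorded as NA". Only a patient with no report at all is stored as missing.

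Section 5 (Statistical analysis – Aim 2) fits the new model by Cox regression and says: "Multiple imputation will be used to replace missing values". The only other routes in Section 5 that touch this kind of problem are:

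- the back-fill of baseline data from hospital episode records, which covers race, hypertension and tobacco;
- two Aim 2 sensitivity analyses, one on treatment for growth and one on unexplained death.

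Neither concerns aneurysm shape, and no re-reading of images is stated for this covariate.

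Section 1 lists irregularity among the predictors that PHASES left out and that motivate Aim 2: "Examples include aspirin use, statin use, smoking, aneurysm irregularity, multiple aneurysms, family history of aneurysms/SAH and polycystic kidney disease". The same section criticises the main earlier cohort because "a disproportionate number of high risk aneurysms (for example with dome irregularity and blebs) were treated before entry to the study".

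**The concern.** The stored value 'absent' has two meanings: the reader described a smooth contour, or the reader did not comment. The merge happens at the site. The coordinating centre cannot undo it, because separating the two later would mean sites reopening the reports. A statistical analysis plan cannot repair it either, since the distinction is not in the data.

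Aim 2 is a primary aim, and the protocol itself treats irregular domes as high risk. If irregular aneurysms sit in the reference group, a weak coefficient could reflect reporting habits and not biology. The predicted risk for aneurysms that really are smooth would also be too high. A clinician who applies the model after looking at the images would be using a coefficient estimated on something else, namely irregularity that a reporter chose to mention.

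**Working it through.** **The plan's own figures.** Section 7.2.1 bases the size on "ISUIA recorded 51 ruptures in 1692 patients over 4.1 years". For the 120 events of Aim 2, 120 × 1692/51 = 3,981 patients, and 3,981 × 4.1 = about 16,323 patient-years (stated: 3,981 and 16,332). These reproduce closely. None depends on the shape rule, and the protocol gives no prevalence of irregularity, no completeness of reporting and no expected HR. Everything below therefore rests on assumed inputs, shown as a range.

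**Dilution.** Let p be the true prevalence of irregularity and s the share of irregular aneurysms that the report mentions. Assume no false positives, and mention unrelated to rupture risk given the other covariates.

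- Share of the absent group that is truly irregular: f = p(1 − s)/(1 − ps)
- Observed HR = HR/(1 + f(HR − 1))
- Overstatement of the smooth-aneurysm rate = f(HR − 1)

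| p | s | f | True HR 2 seen as | True HR 3 seen as |
|---|---|---|---|---|
| 0.15 | 0.7 | 0.045/0.895 = 5.0% | 1.90 | 2.73 |
| 0.15 | 0.3 | 0.105/0.955 = 11.0% | 1.80 | 2.46 |
| 0.20 | 0.5 | 0.100/0.900 = 11.1% | 1.80 | 2.45 |
| 0.30 | 0.7 | 0.090/0.790 = 11.4% | 1.80 | 2.44 |
| 0.30 | 0.3 | 0.210/0.910 = 23.1% | 1.63 | 2.05 |

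The smooth-aneurysm rate is overstated by 5-23% at HR 2 and by 10-46% at HR 3.

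**Power.** Take p = 0.3, s = 0.6, HR 2 and two-sided alpha 0.05, all assumed. With perfect recording, √(120 × 0.3 × 0.7) × ln 2 = 3.48, which gives power of about 94%. Under the rule, 18% are coded present and the observed HR is 1.745, so √(120 × 0.18 × 0.82) × ln 1.745 = 2.34 and power is about 65%. At the full target of 113,905 patient-years the protocol's rate gives about 837 events. Power is then no longer the issue, but the bias remains.

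**When the direction changes.** Suppose p = 0.3, 30% of aneurysms carry three times the baseline risk for other reasons, and mention is 80% in those and 40% in the rest. With a true HR of 2:

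- Rate in the group coded present: (0.3 × 0.8 × 6 + 0.7 × 0.4 × 2)/(0.24 + 0.28) = 2.00/0.52 = 3.85.
- Rate in the group coded absent: (0.738 + 0.742)/0.844 = 1.75.
- Unadjusted ratio: 2.19, above the true 2. Adjustment for size and site removes only the part that those covariates explain.

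**What full imputation would do.** Take p = 0.20, s = 0.5, HR 2, and assume that 10% of smooth aneurysms are explicitly called smooth. Reports that comment on shape are then 0.10 irregular and 0.08 smooth, so 0.10/0.18 = 56% are irregular. Imputation under missing at random, with no other covariates, carries 56% to the whole cohort against a true 20%. The overall rate is 0.8 × 1 + 0.2 × 2 = 1.2 times the smooth rate. Splitting it at 56% with HR 2 gives a smooth rate of 1.2/1.556 = 0.77, an understatement of about 23%. In the same case the current rule overstates it by 11%.

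**The case against.** The strongest defence is that reporters describe shape by exception. A silent report often means that the shape was seen and was unremarkable. The protocol uses the same convention openly for population, on the ground that an exception would be noted. This stands, and it is why silence should not be read as non-assessment. A reader might infer that unassessed aneurysms fill the reference group, but the documents do not say what silence means. They offer no justification for the default on shape, as they do for population.

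A reader might also infer that the HR is certainly diluted. The differential-mention example shows that it need not be.

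Two stronger repairs are tempting. One is to impute every silent report in the main analysis. Silence probably carries information about shape, and the calculation shows that this can lower the predicted risk for smooth aneurysms by more than the current rule raises it. The other is to accept irregularity from MDT records, because size follows a wider hierarchy ("the longest aneurysm dimension recorded to the nearest millimetre as described by the MDT discussion or where not available from the reporting radiologist"). But patients may be seen, scanned or only discussed, so whether an MDT record exists may track consideration of treatment, and treatment ends follow-up. A single source is defensible.

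Three further points stand in part. Aim 2 is prediction, and a predictor defined as reported irregularity gives correct average risk to users who code reports the same way. The covariate is desirable and not core, and Aim 1 does not use it. Finally, the separate data definitions manual is not shown, although the protocol already fixes the stored value.

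**Conclusion.** The point holds as a limited one. The rule discards a distinction that cannot be recovered centrally, and no planned analysis addresses it. If some irregular aneurysms go unmentioned, the irregularity coefficient may be biased: toward 1 if mention is unrelated to rupture risk given the other covariates, and possibly away from 1 if it is related. Under the first condition the rate for smooth aneurysms is overstated.

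The size is unknown from the documents. With assumed prevalence of 15-30%, 30-70% of irregular aneurysms mentioned and no false positives, a true HR of 2 appears as about 1.6-1.9. At the mild end the effect is small. The documents do not show that the Aim 2 model is materially wrong, nor that the current coding should be replaced as the main analysis. This is a cheap improvement to data capture and does not touch the PHASES validation.

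**What to change.** 1. In the protocol and the data definitions manual, record three levels at the site: present; explicitly absent; report available but shape not mentioned. Keep NA for no report.
2. Keep 'not mentioned = absent' as the main Aim 2 coding. It can be recreated exactly from the three levels, so nothing is lost.
3. Add a sensitivity analysis with 'not mentioned' as its own category. A coefficient near that of the stated-smooth group supports the current rule, provided the stated-smooth group is not too small to be informative.
4. Add a missing-not-at-random sensitivity analysis that varies the assumed share of irregular aneurysms among silent reports. Start from 0, which is the current rule, and go to at least 25%. That upper value follows from p = 0.30, s = 0.3 and 10% of smooth shapes stated: 0.21/(0.21 + 0.63) = 25%. Include the outcome in the imputation model, and report the share at which the conclusion on irregularity changes.
5. State in the report that the coefficient describes irregularity as reported, and that it may not carry over to direct image reading.

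The cost is one extra code for data collectors and a few extra model runs. It is cheapest before sites collect data; afterwards it means reopening reports.
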